#### 15.1.1 All Adverse Events

Treatment-emergent AEs will be summarized by dose and overall in tables with:

 The number and percentage of subjects with any TEAE, any IMP-related TEAE, any serious TEAE, any IMP-related serious TEAE, any Grade ≥3 TEAE, any IMP-related Grade ≥3 TEAE, any AEs of special interest (AESI), any TEAE leading to death, any IMP-related TEAE leading to death, any TEAE leading to study discontinuation

- The number and percentage of subjects with at least one TEAE by SOC and PT
- The number and percentage of subjects with at least one TEAE by worst grade, SOC, and PT
- The number and percentage of subjects with at least one IMP-related TEAE by SOC and PT
- The number and percentage of subjects with at least one TEAE by PT only, sorted in decreasing incidence overall
- The number and percentage of subjects with non-serious TEAEs by SOC and PT
- The number and percentage of subjects with at least one AESI recorded by SOC and PT.

Unless otherwise stated, AEs will be displayed with SOC terms and PTs within each SOC term sorted alphabetically.

For determining incidence counts, within each level of TEAE term, if a subject experiences more than one occurrence, the subject will only be counted once for that TEAE.

If an AE is reported for a given subject more than once during treatment, the worst severity and the worst relationship to study treatment will be tabulated.

Adverse events related to IMP are those events with relationship missing, unknown or yes.

In case a subject had events with missing and non-missing severity, the maximum non-missing severity will be displayed.

# 15.1.2 Adverse Events Leading to Study Discontinuation

A listing of TEAEs leading to study discontinuation, if any, will be provided.

# 15.2 Deaths, Other Serious Adverse Events, and Other Significant Adverse Events

### 15.2.1 Deaths

A listing of deaths, if any, will be provided.

## 15.2.2 Serious Adverse Events

A listing of serious AEs (SAEs), if any, will be provided.

## 15.2.3 Other Significant Adverse Event

The following will be considered as AESIs in this study:

Vomiting or diarrhea

- Liver enzyme elevations (alanine aminotransferase [ALT], aspartate aminotransferase [AST], bilirubin)
- Cutaneous reactions (local tolerability measured by severity of redness, swelling, induration, bruising, and itching)
- Photosensitivity/light sensitivity
- Pregnancy in a female partner of a male subject.

These AESIs will be summarized by SOC and PT, as applicable, as specified in Section 15.1.1.

For Part C, the malaria clinical score for treatment initiation will be listed and summarized by dose.

# 15.3 Clinical Laboratory Evaluation

Listings and summary statistics at each assessment time will be presented using the Système International (SI) units. Normal ranges will be provided by the central laboratory, and out of range flags will be calculated based on the normal ranges. Laboratory data not transferred from the central laboratory in SI units will be converted to SI units before processing. Both original units and SI units will be provided in the SDTM domain.

Continuous clinical laboratory data (hematology, biochemistry, coagulation, and urinalysis) will be summarized by dose and time point using descriptive statistics for baseline (see definition in Section 9), each evaluation during the study, and change from baseline to each evaluation.

Box-and-whisker plots for the absolute change from baseline by dose, by time point will also be provided. Placebo data from all cohorts in part A will be pooled.

Listings of all clinical laboratory data for each subject will be provided, with values outside the normal ranges indicated. Listings of abnormal test results (low and high) will be provided.

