During the conduct of the trial, the observed exposure was much lower (factor of 11 to 19) than predicted. The prediction of the efficacious dose was updated to 700 mg (range 600 to 800 mg). Based on the accumulated safety and PK data, the SMC recommended to add 2 additional SAD cohorts of 1,000 mg and (dependent on SMC review) 1,500 mg. Due to observations of transient, increases in liver enzymes above ULN in 4 of 8 subjects (one subject Grade 2 ALT and Grade 1 AST, two subjects Grade 1 for both ALT and AST, and one subject Grade one for ALT – according to Toxicity Grading Scale for healthy volunteers) of the 1,000 mg SAD cohort, the SMC decided to dose the next cohort with an intermediate dose of 1,250 mg.

In case no clinically significant deviations of safety parameters or appearance of any moderate/severe IMP-related TEAEs are observed, the SMC may decide to explore higher doses.

It is envisaged to explore a dose (exposure) up to around 2,400 mg, assuming 3 times the highest anticipated therapeutic dose (exposure) of 800 mg, if feasible without jeopardizing the safety of the subjects in the study.

The SMC will convene at an appropriate time to allow for the compilation of the required data for review. The interval between the completion of IMP administration in one cohort and the initiation of IMP administration in the next cohort of subjects will therefore be minimally 25 days. This will allow sufficient time for an SMC review and the final decision to be communicated to the trial site. Initiation of a higher-dose cohort will only occur if the previous dose level was deemed to be generally safe and well-tolerated and is predicted not to exceed the maximum exposure (see Section 5.5).

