- Recovered without sequelae
- Recovered with sequelae
- Ongoing
- Fatal
- Unknown.

In case of a fatality, the cause of death is considered as the SAE, and the death is considered as its OUTCOME.

Abnormal Laboratory Findings and Other Abnormal Investigational Findings

Abnormal laboratory findings and other abnormal investigational findings should not be reported as AEs unless they are associated with clinical signs and symptoms, lead to treatment discontinuation or are considered otherwise medically important by the Investigator. If a laboratory abnormality fulfills these criteria, the identified medical condition must be reported as the AE rather than the abnormal value itself.

Serious Adverse Events

An SAE is any untoward medical occurrence that at any dose:

- Results in death
- Is life-threatening. (Note: The term “life-threatening” refers to an event in which the subject is at risk of death at the time of the event, not an event that hypothetically might have caused death if it was more severe)
- Requires inpatient hospitalization or prolongs an existing hospitalization
- Results in persistent or significant disability or incapacity
- Is a congenital anomaly or birth defect

- Is otherwise considered to be medically important. (Note: Important medical events that may not result in death, be life-threatening, or require hospitalization may be considered as SAEs when, based upon appropriate medical judgment, they may jeopardize the subject or may require medical or surgical intervention to prevent one of the outcomes listed above. Examples of such events include allergic bronchospasm requiring intensive treatment in an emergency room or at home, blood dyscrasias or convulsions that do not result in inpatient hospitalization, or the development of drug dependency or drug abuse).

For the purposes of reporting, any suspected transmission of an infectious agent via an IMP/inoculum is also considered an SAE and should be reported in an expedited manner, as described in Section 7.4.1.4.

Events that Do Not Meet the Definition of an SAE

Elective hospitalizations to simplify trial treatment or trial procedures (for example, an overnight stay to monitor initiation of treatment with the IMP is not considered an SAE. However, all events leading to unplanned hospitalizations or unplanned prolongation of an elective hospitalization (for example, undesirable effects of any administered treatment) must be documented and reported as SAEs.

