8.5.2 Analysis of Primary Endpoints

8.5.2.1 Safety

Part A and Part B

Safety data analysis will be conducted on the Safety Analysis Set. The number and percentage of subjects experiencing one or more AEs will be summarized by dose level group, relationship to IMP, and severity. AEs will be coded using Medical Dictionary for Regulatory Activities terminology. Laboratory parameters will be summarized using descriptive statistics, by postdose shifts relative to baseline, and data listings of abnormal results as appropriate. Vital signs and ECG data will be summarized for observed and changes-from-baseline values by dose level using descriptive statistics. Clinically noteworthy ECG findings for individual subjects will be listed and summarized as appropriate.

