#### 4 Purpose of the Integrated Analysis Plan

The purpose of this Integrated Analysis Plan (IAP) is to document technical and detailed specifications for the final analysis of data collected for Clinical Study Protocol MS201618-0013. Results of the analyses described in this IAP will be included in the Clinical Study Report (CSR). Additionally, the planned analyses identified in this IAP will be included in regulatory submissions or future manuscripts. Any post-hoc, or unplanned analyses performed to provide results for inclusion in the CSR but not identified in this prospective IAP will be clearly identified in the CSR.

The IAP is based upon the Clinical Study Protocol Version 5.0 including Amendment 4 and is prepared in compliance with International Council for Harmonisation (ICH) E9. It focuses on the detailed description of the statistical analyses for safety, pharmacokinetics (PK), pharmacodynamics (PD), and other variables. Part B of the study (multiple ascending doses [MAD]) is designated as optional in the protocol and will not be conducted, so the analysis is not currently defined in this IAP.

#### Objectives and Endpoints 5

The objectives and endpoints below pertain to Part A and Part C only.

|                         | Objective  | Endpoint  | IAP
Section |
|-------------------------|--|---|----------------|
| PART A                  |  |   |                |
| Primary
Objective    | To investigate the safety and tolerability of single ascending oral doses of M5717 | Primary Endpoints  Nature, incidence, and severity of AEs/SAEs, including relationship to study treatment, AEs/SAEs leading to dose modification or discontinuation of study treatment  Incidence of clinically significant changes and abnormalities in safety laboratory parameters (hematology, coagulation, biochemistry [specifically ALT and AST], and urinalysis)  Incidence of clinically significant changes and abnormalities in vital signs (body temperature, BP, heart rate, and respiratory rate) and 12-lead ECG | 15             |

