## Tables and Descriptive Statistics

All data will be summarized by study part, dose group, day, and/or nominal time point, as appropriate. Data for subjects who received placebo will be pooled across dosing cohorts belonging to the same trial part. Repeated and unscheduled measurements included in the listings will not be used for statistical analyses or summaries, unless the repeated measurement was performed due to unreliable values/technical reasons, eg, clotted samples.

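### SAP 15.3 plans no count of affected subjects and no shift summary for the Part A primary laboratory endpoint, and SAP section 9 keeps unscheduled results out of every summary

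*SAP*

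**What the plan says.** - **Endpoint.** SAP section 5 gives as a Part A primary endpoint "Incidence of clinically significant changes and abnormalities in safety laboratory parameters (hematology, coagulation, biochemistry [specifically ALT and AST], and urinalysis" and points to SAP section 15 for the analysis. The same endpoint is secondary in Part C.
- **Protocol analysis (8.5.2.1).** "Laboratory parameters will be summarized using descriptive statistics, by postdose shifts relative to baseline, and data listings of abnormal results as appropriate". For ECG, the same section also wants noteworthy individual findings listed and, where suitable, summarized.
- **SAP analysis (15.3).** "Continuous clinical laboratory data (hematology, biochemistry, coagulation, and urinalysis) will be summarized by dose and time point using descriptive statistics", at baseline and each evaluation and as change from baseline, with box plots of the change. It adds: "Listings of all clinical laboratory data for each subject will be provided, with values outside the normal ranges indicated", plus a separate listing of abnormal results.
- **SAP section 9.** Descriptive statistics for safety data are n, mean, SD, median, quartiles, minimum and maximum. On extra samples it says: "Repeated and unscheduled measurements included in the listings will not be used for statistical analyses or summaries". The one exception is a repeat done because a result was not reliable or for a technical reason such as clotting.
- **SAP section 7.** The declared changes from the protocol are the removal of the 24-hour AUC parameters and the added dried-blood-spot correlation. Laboratory shifts are not mentioned.
- **AESI route.** SAP 15.2.3 makes ALT, AST and bilirubin elevations an AESI without a cut-off, and SAP 15.1.1 tabulates AESIs by subject. Protocol 7.4.1.1 says abnormal laboratory findings "should not be reported as AEs unless they are associated with clinical signs and symptoms", lead to discontinuation, or are judged medically important by the investigator.
- **Known signal.** For the 1,000 mg cohort, protocol 5.2.2 reports "increases in liver enzymes above ULN in 4 of 8 subjects".

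**The concern.** An incidence needs a numerator and a denominator in subjects. By-visit statistics describe the distribution at one time. They do not say how many subjects crossed a limit at any time after dosing, and that is what the endpoint asks. The protocol's shift summary would have come closest, and the SAP leaves it out without saying so.

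The rule on unscheduled values adds to this. Protocol 7.4.3.1 allows extra laboratory tests at the investigator's discretion, and protocol 7.1.6 has unacceptable values followed until they resolve, so off-schedule results are foreseeable. Under SAP section 9 they would be listed but not summarized.

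At stake is the clarity of a named primary safety endpoint in a first-in-human trial in which ALT and AST have already influenced dose escalation. SAP section 4 says analyses outside the plan will be identified as such in the study report. An incidence table added later would therefore carry the label of an unplanned analysis, although it addresses a primary endpoint.

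**Working it through.** The documents give no sample-size, power or precision figure to reproduce for this endpoint. The check is a comparison of text with three small calculations.

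**1. What is required and what is planned**

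| Element | Protocol 8.5.2.1 | SAP 15.3 with section 9 |
|---|---|---|
| By-visit descriptive statistics | yes | yes |
| Listing of abnormal results | yes | yes |
| Postdose shift from baseline | yes | absent, not declared in section 7 |
| Subjects with an abnormal or clinically significant value | implied by the endpoint | absent |
| Worst postdose value, all samples | not stated | absent; unscheduled values barred from summaries |

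SAP section 9 has a general rule that qualitative variables get counts and percentages. No laboratory category is named for it to act on.

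**2. The figure that an incidence table would show**

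Inputs from protocol 5.2.2: one subject with Grade 2 ALT and Grade 1 AST, two with Grade 1 for both, one with Grade 1 ALT; allocation 6 active to 2 placebo.

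- ALT raised: 1 + 2 + 1 = 4 subjects, which agrees with the protocol's 4 of 8. AST raised: 1 + 2 = 3.
- The split by arm is not given. At most 2 of the 4 can be on placebo, so the active count lies between 4 − 2 = 2 and 4.
- Exact (Clopper-Pearson) 95% limits: lower = Beta quantile(0.025; x, n − x + 1), upper = Beta quantile(0.975; x + 1, n − x).

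| x/n | Proportion | Exact 95% CI |
|---|---|---|
| 4/8, both arms | 50% | 15.7% to 84.3% |
| 2/6, active | 33% | 4.3% to 77.7% |
| 3/6, active | 50% | 11.8% to 88.2% |
| 4/6, active | 67% | 22.3% to 95.7% |

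The intervals show how little one cohort says about incidence. They do not measure harm caused by the SAP. The point is that no table in 15.3 contains any of these counts or sets them beside pooled placebo.

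**3. What by-visit statistics show (assumed values)**

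Assume 6 active subjects, all at 0.5 × ULN unless stated.

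- One subject peaks at 3 × ULN at a scheduled visit: mean = (3 + 5 × 0.5)/6 = 0.92 × ULN, median 0.5, maximum 3.0. The maximum shows the peak.
- The same peak is seen only at an unscheduled draw: mean, median and maximum all stay at 0.5 × ULN. Only the listing shows it.
- Two subjects peak at 2 × ULN at the same scheduled visit: mean = (2 × 2 + 4 × 0.5)/6 = 1.0.
- Two subjects peak at 2 × ULN at different scheduled visits: mean = (2 + 5 × 0.5)/6 = 0.75 at each, with a maximum of 2.0 at each. The table looks the same whether one subject peaked twice or two subjects peaked once.

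**4. Whether the AESI table supplies the incidence**

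Only in part. It counts subjects by dose, but a raised value enters only if the investigator reports it as an event. No cut-off is given, and protocol 7.4.1.1 limits reporting of isolated abnormalities. Hematology, coagulation, urinalysis and the rest of biochemistry are outside its laboratory item.

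**The case against.** The best defence is that nothing is hidden. Cohorts have 8 subjects, every laboratory value is listed with out-of-range flags, and abnormal results are listed again. Minimum and maximum are tabulated at each scheduled visit, and Part A schedules biochemistry often. Liver enzyme elevation is an AESI that must be reported within 24 hours even if nonserious, and it has its own incidence table. Clinically significant findings in other parameters can reach the TEAE tables, including the one by worst grade. The 1,000 mg signal was in fact seen and acted on by the SMC, whose analyses follow its own charter. The trial is descriptive, and the protocol attaches the words "as appropriate" to its laboratory summaries.

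Most of this stands, and it rules out several stronger readings that a reader might infer:

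- **That the ALT/AST signal could vanish from the report.** It could not, because the listings keep every value, including unscheduled ones.
- **That the report would hold no number at all for the endpoint.** Reported liver AESIs and other TEAEs are counted. What is missing is an incidence based on measured values.
- **That vital signs and ECG lost a shift analysis too.** Protocol 8.5.2.1 asks for observed and change-from-baseline statistics there, and SAP 15.4 and 15.5.1 provide them. What is not carried over is the summary of noteworthy ECG findings. Their own incidence endpoint also has no count.
- **That the protocol's QTcF limit of 450 ms, or its ULN multiples, define a postdose abnormality.** The first is an exclusion criterion (protocol 5.3.2.1); the second are withdrawal criteria (protocol 5.5.1 and 5.5.2).
- **That confidence intervals are required.** Protocol 8.5.1 plans no formal hypothesis testing, so they are optional.

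The defence does not answer the central point. Listings let a reader reconstruct an incidence by hand, but they are not a planned analysis of it. The AESI count depends on reporting judgement, not on the measurement.

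**Conclusion.** The concern holds as a reporting gap. For a Part A primary endpoint defined as an incidence, SAP 15.3 plans no subject count from measured values, and it drops the protocol's postdose shift summary without declaring the change. SAP section 9 then keeps off-schedule elevations out of all laboratory summaries, technical repeats aside. The ALT/AST signal can therefore be understated in, or missing from, the laboratory summary tables, though it remains in the listings.

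The size is best seen in the 1,000 mg cohort: 4 of 8 subjects, hence 2/6 to 4/6 on active drug, for which 15.3 has no row. This range assumes that the 6:2 allocation was achieved in that cohort. How many elevations will be seen only off schedule cannot be estimated from the documents. With frequent scheduled biochemistry in Part A, it may be few.

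**What to change.** In SAP 15.3 add, by dose and pooled placebo (by dose alone in Part C, which has no placebo):

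1. The shift summary of protocol 8.5.2.1, from baseline to the worst postdose value.
2. The count and percentage of subjects by worst postdose category. Use the out-of-range flag for all parameters and, for ALT, AST and bilirubin, toxicity grade or ULN multiple. Label these as reporting categories only.

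Both should use scheduled, unscheduled and repeat results. In SAP section 9, limit the exclusion of repeat and unscheduled values to by-visit descriptive statistics.

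In SAP 15.5.1, carry over the protocol's summary of clinically noteworthy ECG findings. In 15.4 and 15.5.1, add the count of subjects with a value judged clinically significant, and say who makes that judgement. Do not present 450 ms as the protocol's postdose definition. Exact intervals for ALT and AST may be added but are not needed.

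If the shift summary is left out on purpose, SAP section 7 should say so and why.

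The cost is SAP wording and a few extra tables from data already collected, with no change to trial conduct.

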# 15.4 Vital Signs

Vital signs data will be summarized by dose and time point using descriptive statistics for baseline (see definition in Section 9), each evaluation during the study, and change from baseline to each evaluation. Listing of vital signs data will be provided.

# 15.5 Other Safety or Tolerability Evaluations

# 15.5.1 12-lead Electrocardiogram

Safety ECG data will be summarized by dose and time point using descriptive statistics for baseline (see definition in Section 9), each evaluation during the study, and change from baseline to each evaluation. Listing of safety ECG data will be provided.

# 16 Analyses of Other Endpoints

### 16.1 Pharmacokinetics

# 16.1.1 Handling of Blood, Urine, and Fecal Concentrations

### 16.1.1.1 Whole Blood

Concentrations of M5717 in whole blood will be measured in all cohorts in Parts A and C. Additionally, concentrations of M5717 metabolites may be measured in whole blood from male subjects receiving M5717 treatment in Part A (all cohorts).

Predose samples that occur before drug administration will be assigned a time of 0 hours, as if the sample had been taken simultaneously with the study drug administration.

Concentration values below the lower limit of quantification of the assay (LLOQ) will be taken as zero for summary statistics of PK concentration data.

In case of concentrations above the upper limit of quantification (ULOQ), the concentration will be set to missing.

Missing concentrations (eg, no sample, insufficient sample volume for analysis, no result or result not valid) will be reported and used generally as no result ("NR").

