### Handling of Missing Data

Unless otherwise specified, missing data will not be replaced.

Handling of missing data for PK parameter calculations are discussed under Section 16.1.

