# 16.1.2 Derivation of Individual Whole Blood, Urine, and Fecal Pharmacokinetic Parameters

### 16.1.2.1 Whole Blood

Pharmacokinetic parameters will be calculated b PPD using standard non-compartmental methods and the actual administered dose. PK parameters will be calculated using the actual

elapsed time since dosing, given with a precision of 14 significant digits. In cases where the actual sampling time is missing, calculations will be performed using the nominal time. Otherwise, there will be no further imputation of missing data.

The following parameters will be calculated from M5717 whole blood concentrations in Part A and Part C. If M5717 whole blood metabolite concentrations are available in Part A, parameters may also be calculated for these metabolites (if applicable, and if sufficient data are available).

| Symbol                         | Definition  |
|--------------------------------|---|
| AUC 0-t             | The AUC from time zero (= dosing time) to the last sampling time (t last ) at which the concentration is at or above the lower limit of quantification. Calculated using the mixed log linear trapezoidal rule (linear up, log down).  |
| AUC 0-t /Dose       | The dose-normalized $AUC_{0-t}$ . Normalized using the actual dose, using the formula $AUC_{0-t}/Dose$ .  |
| AUC 0-144h          | The AUC from time zero (= dosing time) to 144 hours postdose. Calculated using the mixed log linear trapezoidal rule (linear up, log down).   |
| AUC 0-144h
/Dose | The dose-normalized AUC $_{0-144h}$ . Normalized using the actual dose, using the formula AUC $_{0-144h}$ /Dose.  |
| AUC 0-∞             | The AUC from time zero (dosing time) extrapolated to infinity, based on the predicted value for the concentration at $t_{last}$ , and estimated using the linear regression from the determination of the terminal first order (elimination) rate constant ( $\lambda_z$ ). AUC 0-<math>\infty</math> = AUC 0-<math>\tau</math> +C last pred / $\lambda_z$ . |
| AUC 0-∞ /Dose       | The dose-normalized AUC0- $\infty$ . Normalized using actual dose, using the formula AUC0- $\infty$ /Dose.  |
| AUC extra %         | The AUC from time $t_{last}$ extrapolated to infinity given as percentage of AUC 0-<math>\infty</math> . AUC extra % = (extrapolated area/AUC 0-<math>\infty</math> )*100.   |

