| $\mathrm{CL}_{\mathrm{f}}$     | The apparent total body clearance of drug following extravascular administration, taking into account the fraction of dose absorbed. $CL/f = Dose /AUC_{0-\infty}$ . Calculated for M5717 only.   |
| $C_{max}$                      | Maximum observed concentration.   |

24/31

| Symbol                    | Definition  |
|---------------------------|---|
| C max
/Dose | The dose-normalized $C_{\text{max}}$ . Normalized using the actual dose, and the formula $C_{\text{max}}/\text{Dose}$ .   |
| $\lambda_z$               | Terminal first order (elimination) rate constant. Determined from the terminal slope of the log-transformed concentration curve using linear regression on terminal data points of the curve.   |
| t 1/2          | Apparent terminal half-life. $t_{1/2} = \ln (2)/\lambda_z$ .  |
| t max          | The time to reach the maximum observed concentration collected during a dosing interval (in case of multiple/identical C max values, the first occurrence will be used).   |
| $V_{\mathrm{Z/f}}$        | The apparent volume of distribution during the terminal phase following extravascular administration, based on the fraction of dose absorbed. $V_{z/f} = Dose/(AUC_{0-\infty}*\lambda_z)$ following single dose. Calculated for M5717 only. |
| t>3 ng/mL                 | Time above or equal to the predicted M5717 mouse minimum inhibitory concentration (MIC) of 3 ng/mL.   |
| t>10 ng/mL                | Time above or equal to the predicted M5717 mouse minimal parasiticidal concentration (MPC) of 10 ng/mL.   |

For  $CL_{\rm ff}$  and  $V_{\rm Z/f}$  and all dose-normalized parameters, the actual M5717 dose after adjustment for molecular weight differences between salt and free base form will be used for calculation of these parameters (ie, Adjusted dose = Dose \* 462.56/580.65), where 462.56 and 580.65 are the molecular weights of the M5717 free base and succinate salt, respectively.

The following PK parameters will be calculated for diagnostic purposes and listed for Part A and Part C, but will not be summarized:

- The time interval (h) of the log-linear regression (λz low, λz upp) to determine λz.
- Number of data points (Nλ) included in the log-linear regression analysis to determine λz.
- Goodness of fit statistic (Rsq) for calculation of λz.

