# Statistical Analysis

All PK whole blood concentrations including dried blood spot assay concentrations, and whole blood PK parameters will be descriptively summarized by trial part, analyte, and dose group as described above. A listing of PK blood sample collection times as well as derived sampling time deviations will also be provided.

PK urine and fecal sample collection start and stop times, and urine volumes and fecal weights will be listed.

Individual whole blood concentration-time profiles by trial part, analyte, and dose group will be created using the actual time points and the numeric concentration data. These figures will include plots of all subjects in the same dose group on the same plot (spaghetti plots), as well as separate plots for individual subjects (by-subject plots). Arithmetic mean whole blood concentration-time profiles by trial part, analyte, and dose group will be provided using nominal time points and the numeric concentration data. All concentration-time plots for PK data will be presented both on a linear and on a semi-logarithmic scale. Mean plots will include SD error bars when plotted on a linear scale.

Linear scatter plots of individual and geometric mean values of non-normalized and dosenormalized parameters [AUC0-∞, AUC0-1, AUC0-144h, and Cmax] versus M5717 dose (on continuous scale) will be prepared, as appropriate. Box plots of the dose-normalized parameters versus M5717 dose (on continuous scale) will be prepared. When applicable, parameters from Part A and Part C will be combined on the same plot (for scatter plots, different symbols will be used for data from the different study parts). Otherwise, plots will be prepared separately by trial part, as applicable.

The analysis of dose proportionality of single-dose PK parameters of M5717 will be quantified as part of an exploratory analysis using the power model on the original parameters (ln[PK parameter]=  $\alpha + \beta \times \ln[\text{dose}]$ ). This analysis will be based on AUC0-\infty, AUC0-1, AUC0-144h, and Cmax in Part A and Part C. The intercept  $\alpha$  and the slope  $\beta$  together with 90% CIs will be estimated and presented. A p-value testing whether  $\beta = 1$  will also be presented. For a given parameter, a minimum of 3 values must be available for a dose level, for that dose level to be included in the dose proportionality analysis.

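### Setting concentrations above the ULOQ to missing understates Cmax, and generally AUC, whenever the rule is applied; the documents do not show how often that would be

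*SAP*

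**What the plan says.** SAP 16.1.1.1 (Whole Blood) gives the rule: "In case of concentrations above the upper limit of quantification (ULOQ), the concentration will be set to missing". The next sentence of that section reads: "Missing concentrations (eg, no sample, insufficient sample volume for analysis, no result or result not valid) will be reported and used generally as no result". An above-range result is therefore not distinguished from a sample that was lost or failed.

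Nothing restores the value later. SAP section 9 says "Unless otherwise specified, missing data will not be replaced". SAP 16.1.2.1, after allowing nominal times where actual times are missing, adds "Otherwise, there will be no further imputation of missing data".

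The same section defines Cmax as "Maximum observed concentration" and computes AUC by the linear-up, log-down trapezoidal rule. Its quality flags cover the fit and span of the terminal regression and the extrapolated share of AUC. None of them reacts to a missing peak.

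Cmax, AUC0-inf, AUC0-t and AUC0-144h from Parts A and C then enter SAP 16.1.3: "The analysis of dose proportionality of single-dose PK parameters of M5717 will be quantified as part of an exploratory analysis using the power model". The slope is reported with a 90% CI and a p-value for slope equal to 1. A dose level needs at least three values, and a Cmax or AUC computed after deletion counts as one.

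**The concern.** The rule selects on the outcome. A sample is removed only because its concentration is high, so the missingness is fully informative and the error in Cmax has one direction. It also conflicts with SAP 10.2.1, under which a concentration that merely looks implausible must stay in the analysis. A doubtful value is kept, while a value known to be high is dropped.

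PK parameters are a primary endpoint of Part C (Protocol 8.3.1) and the secondary endpoint of Part A (Protocol 8.3.2). At stake are the reported peak and total exposure in the most exposed subjects of a first-in-human trial, and the description of how exposure rises with dose. The listings would show a gap, but not why it is there, and the affected parameters would carry no mark.

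**Working it through.** The documents give no ULOQ, no expected count of samples above it and no bias estimate, so there is no stated figure to reproduce. I checked direction first, then size under stated assumptions.

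**Direction**

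1. Every deleted value exceeds the ULOQ and every retained value is at or below it. The maximum of the retained values is therefore below the true maximum. If the true peak is 1.5 × ULOQ, reported Cmax is at least 1 − 1/1.5 = 33% too low for that subject.
2. Take retained neighbours a and c, both at or below the ULOQ, around a deleted value b above it. The bridge from a to c never exceeds the larger of the two. The path through b lies above that bridge over the whole interval, whether c is larger or smaller than a. So AUC0-t and AUC0-144h fall when samples on both sides are kept. AUC0-inf also falls if the terminal rate constant is unchanged.
3. Under dose-related exposure, samples above the ULOQ occur mostly at the top doses. Lowering the right-hand end of ln(parameter) = α + β × ln(dose) lowers β.

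**Size, by simulation of the SAP's rule**

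Taken from the documents: Part A sampling times (Protocol Table 1), six active subjects per cohort (Protocol 8.2), the trapezoidal rule and the power model.

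Assumed: doses of 50, 100, 200, 400, 600, 1,000 and 1,250 mg; true β = 1; between-subject CV 30%; residual CV 10%; 400 replicates. Two curve shapes were used: a narrow peak (tmax about 4 h, two-phase decline) and a broad peak (tmax about 16 h, half-life 150 h). The ULOQ was varied as a multiple of the median Cmax at 1,250 mg. Part C subjects are not included.

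| ULOQ ÷ median Cmax at 1,250 mg | 1,250 mg subjects affected | Geometric-mean Cmax at 1,250 mg | Cmax slope, full data → SAP rule |
|---|---|---|---|
| 2 | 2% | −0.3% to −0.4% | 1.000 → 1.000; 0.998 → 0.998 |
| 1.5 | 13% to 15% | −2.5% to −3.1% | 1.000 → 0.995; 0.998 → 0.992 |
| 1.0 | 57% to 64% | −16.8% to −18.5% | 1.002 → 0.962; 0.997 → 0.952 |
| 0.75 | 88% to 90% | −34% to −37% | 1.003 → 0.901; 0.999 → 0.887 |

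The first figure in each pair is the narrow curve and the second the broad one. With the ULOQ equal to the median, the slope falls by 1.002 − 0.962 = 0.040 and 0.997 − 0.952 = 0.045. A longer run of 1,500 replicates gave Cmax losses of 17% and 19% in that row, so these figures are good to about one percentage point.

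**AUC0-144h.** In the same row the loss is about 3% for the narrow curve. For the broad curve it is 13% if the area stops at the last retained sample before 144 h. It is about 8% if the gap is bridged to the next retained sample, which is how a trapezoidal rule would treat it. I use 3% to 8%. With the ULOQ at 1.5 times the median, the AUC0-144h loss is 0.3% to 1%.

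**The case against.** The strongest reply is that the rule may never apply. It acts only on final reported results. Protocol 7.5.1.1 leaves assay detail to a separate bioanalytical report, and dilution of high samples may already be provided for there. Exposure was 11 to 19 times below prediction (Protocol 5.2.2). At 1,250 mg, assuming proportionality, it would be (1,250/600)/19 = 0.11 to (1,250/600)/11 = 0.19 of what was once predicted at the initial 600 mg maximum. An assay range set on those predictions might never be exceeded. All of this stands as a limit on size and likelihood. It does not make the sentence right: if dilution is planned, the SAP should say so and confine its rule to samples that could not be re-assayed.

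Three stronger readings are tempting, and the documents do not support them.

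- **That the rule distorts dose escalation.** SAP 6.1 leaves the methods for Safety Monitoring Committee reviews to the committee's charter, and SAP 6.2 covers the final analysis after database lock. The exposure criterion in Protocol 5.5.3 is a projected group mean AUC0-t, not Cmax.
- **That the slope would breach an 80–125% proportionality band.** The SAP sets no such band. The analysis is exploratory, and Protocol 8.5.1 rules out formal hypothesis testing.
- **That every subject in the top cohort peaks at 1.5 × ULOQ.** This would move the Cmax slope by 1.382 × ln(1/1.5)/8.62 = −0.065, where 1.382 is the top dose's deviation from the mean ln-dose and 8.62 the sum of squared deviations. Under proportionality, 1,000 mg would then peak at 1.5 × 1,000/1,250 = 1.2 × ULOQ, so the top cohort could not be affected alone. The dose set is also an assumption: Protocol 5.2.2 leaves some steps open and allows up to 11 levels.

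**Conclusion.** The point holds in a conditional form. Whenever a final result exceeds the ULOQ, the stated rule understates that subject's Cmax, generally understates AUC by less, and pulls the power-model slope down. This follows from the SAP's own definitions and no other section corrects it.

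The size is unknown because the ULOQ is not given. Under the assumed curves it runs from almost nil, with the ULOQ at least twice the median top-dose Cmax, to about 17 to 18% on top-dose Cmax and 0.04 to 0.05 on its slope, with the ULOQ equal to that median. It would be larger with a lower ULOQ. These figures rest on the assumed doses, variability and curve shapes, and on leaving out Part C, whose subjects also enter the power model. The rule may have no practical effect in this trial. It is still worth correcting, because it can only err towards lower reported exposure and the correction is small.

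**What to change.** Replace the ULOQ sentence in SAP 16.1.1.1 along these lines:

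- Samples above the ULOQ are diluted and re-assayed within the validated range, with a cross-reference to the bioanalytical method.
- Where re-assay is impossible, the result is coded >ULOQ, not NR, and the ULOQ is used as a lower bound in the profile.
- Cmax and AUC from such profiles are flagged as lower bounds in listings and summaries.
- The exploratory power model is run with and without the flagged values, or with those values treated as right-censored.

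Carrying the ULOQ lessens the bias without removing it. Reported Cmax then equals the ULOQ, which is still below the truth but never below what deletion gives. In the 1,500-replicate run with the ULOQ equal to the median, the Cmax loss went from 17% to 14% (narrow curve) and from 19% to 17% (broad curve). Re-assay is therefore the main remedy and the lower bound is the fallback.

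The cost is a short SAP edit, one extra result code and one extra model run if any value is flagged. Re-assay uses the sample already collected, provided enough volume remains. If no sample exceeds the ULOQ, no result changes.
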